8.5. Evaluating of Adverse Events

An Investigator who is a qualified physician will evaluate all adverse events with respect to the elements outlined in [Table 6](#). The Investigator's assessment of causality is required for each adverse event. Refer to [Table 6](#) for instructions in evaluating adverse events.

Table 6. Evaluating Adverse Events

Maximum Intensity	Mild	awareness of sign or symptom, but easily tolerated (for pediatric trials, awareness of symptom, but easily tolerated)
	Moderate	discomfort enough to cause interference with usual activity (for pediatric trials, definitely acting like something is wrong)
	Severe	incapacitating with inability to work or do usual activity (for pediatric trials, extremely distressed or unable to do usual activities)
Seriousness	A serious adverse event (AE) is any adverse event occurring at any dose or during any use of Sponsor's product that:	
	† Results in death; or	
	† Is life threatening; or places the subject, in the view of the Investigator, at immediate risk of death from the event as it occurred [Note: This does not include an adverse event that, had it occurred in a more severe form, might have caused death.]; or	
	† Results in a persistent or significant disability/incapacity (substantial disruption of one's ability to conduct normal life functions); or	
	† Results in or prolongs an existing inpatient hospitalization (hospitalization is defined as an inpatient admission, regardless of length of stay, even if the hospitalization is a precautionary measure for continued observation. (Note: Hospitalization for an elective procedure to treat a pre-existing condition that has not worsened is not a serious adverse event. A pre-existing condition is a clinical condition that is diagnosed prior to the use of a Merck product and is documented in the patient's medical history)); or	
	† Is a congenital anomaly/birth defect (in offspring of subject taking the product regardless of time to diagnosis); or	
	Is a cancer; or	
	Is associated with an overdose (whether accidental or intentional). Any adverse event associated with an overdose is considered a serious adverse event. An overdose that is not associated with an adverse event is considered a non-serious event of clinical interest and must be reported within 24 hours.	
	Other important medical events that may not result in death, not be life threatening, or not require hospitalization may be considered a serious adverse event when, based upon appropriate medical judgment, the event may jeopardize the subject and may require medical or surgical intervention to prevent one of the outcomes listed previously (designated above by a †).	

Table 6. Evaluating Adverse Events

Duration	Record the start and stop dates of the adverse event. If less than 1 day, indicate the appropriate length of time and units	
Action taken	Did the adverse event cause the Sponsor's product to be discontinued?	
Relationship to Sponsor's Product	
Did the Sponsor's product cause the adverse event? The determination of the likelihood that the Sponsor's product caused the adverse event will be provided by an Investigator who is a qualified physician. The Investigator's signed/dated initials on the source document or worksheet that supports the causality noted on the AE form, ensures that a medically qualified assessment of causality was done. This initialed document must be retained for the required regulatory time frame. The criteria below are intended as reference guidelines to assist the Investigator in assessing the likelihood of a relationship between the test drug and the adverse event based upon the available information.
 
The following components are to be used to assess the relationship between the Sponsor's product and the AE; the greater the correlation with the components and their respective elements (in number and/or intensity), the more likely the Sponsor's product caused the adverse event:
	
Exposure		Is there evidence that the subject was actually exposed to the Sponsor's product such as: reliable history, acceptable compliance assessment (pill count, diary, etc.), expected pharmacologic effect, or measurement of drug/metabolite in bodily specimen?
Time Course		Did the AE follow in a reasonable temporal sequence from administration of the Sponsor's product? Is the time of onset of the AE compatible with a drug-induced effect (applies to trials with investigational medicinal product)?
Likely Cause		Is the AE not reasonably explained by another etiology such as underlying disease, other drug(s)/vaccine(s), or other host or environmental factors
Relationship to Sponsor's Product (continued)	
The following components are to be used to assess the relationship between the Sponsor's product and the AE: (continued)
 
Dechallenge
 
Was the Sponsor's product discontinued or dose/exposure/frequency reduced?
 
If yes, did the AE resolve or improve?
 
If yes, this is a positive dechallenge. If no, this is a negative dechallenge.
 
(Note: This criterion is not applicable if: (1) the AE resulted in death or permanent disability; (2) the AE resolved/improved despite continuation of the Sponsor's product; (3) the trial is a single-dose drug trial); or (4) Sponsor's product(s) is/are only used one time.)
	

Table 6. Evaluating Adverse Events

	Rechallenge	
Was the subject re-exposed to the Sponsor's product in this trial? If yes, did the AE recur or worsen? If yes, this is a positive rechallenge. If no, this is a negative rechallenge.
 
(Note: This criterion is not applicable if: (1) the initial AE resulted in death or permanent disability, or (2) the trial is a single-dose drug trial); or (3) Sponsor's product(s) is/are used only one time.)
 
NOTE: IF A RECHALLENGE IS PLANNED FOR AN ADVERSE EVENT WHICH WAS SERIOUS AND WHICH MAY HAVE BEEN CAUSED BY THE SPONSOR'S PRODUCT, OR IF RE-EXPOSURE TO THE SPONSOR'S PRODUCT POSES ADDITIONAL POTENTIAL SIGNIFICANT RISK TO THE SUBJECT THEN THE RECHALLENGE MUST BE APPROVED IN ADVANCE BY THE U.S. CLINICAL MONITOR AND THE INSTITUTIONAL REVIEW BOARD/INDEPENDENT ETHICS COMMITTEE.

	Consistency with Trial Treatment Profile	Is the clinical/pathological presentation of the AE consistent with previous knowledge regarding the Sponsor's product or drug class pharmacology or toxicology?
The assessment of relationship will be reported on the case report forms /worksheets by an Investigator who is a qualified physician according to his/her best clinical judgment, including consideration of the above elements.		
Record one of the following:		Use the following scale of criteria as guidance (not all criteria must be present to be indicative of a Sponsor's product relationship).
Yes, there is a reasonable possibility of Sponsor's product relationship.		There is evidence of exposure to the Sponsor's product. The temporal sequence of the AE onset relative to the administration of the Sponsor's product is reasonable. The AE is more likely explained by the Sponsor's product than by another cause.
No, there is not a reasonable possibility of Sponsor's product relationship		Subject did not receive the Sponsor's product OR temporal sequence of the AE onset relative to administration of the Sponsor's product is not reasonable OR there is another obvious cause of the AE. (Also entered for a subject with overdose without an associated AE.)

8.6. Events of Clinical Interest

Selected non-serious and serious adverse events are also known as Events of Clinical Interest (ECI) and must be recorded as such on the Adverse Event case report forms/worksheets and reported within 24 hours to Pfizer or designee either by electronic media or paper. Appropriate contact information can be found in the Investigator Trial File Binder (or equivalent).

Events of clinical interest for this trial include:

1. An overdose of Sponsor's product, as defined in [Section 8.2](#), that is not associated with clinical symptoms or abnormal laboratory results.
2. An elevated AST or ALT lab value that is greater than or equal to 3X the upper limit of normal and an elevated total bilirubin lab value that is greater than or equal to 2X the upper limit of normal and, at the same time, an alkaline phosphatase lab value that is less than 2X the upper limit of normal, as determined by way of protocol-specified laboratory testing or unscheduled laboratory testing.*

*Note: These criteria are based upon available FDA (Food and Drug Administration) regulatory guidance documents. The purpose of the criteria is to specify a threshold of abnormal hepatic tests that may require an additional evaluation for an underlying etiology. The trial site guidance for assessment and follow up of these criteria can be found in the Investigator Trial File Binder (or equivalent).

8.7. Management of Subjects with Elevated Liver Enzymes (ALT or AST \geq 3X ULN)

Section I: Identification and Management of Subjects with ALT or AST Results \geq 3X ULN

Increases in ALT or AST \geq 3X the upper limit of normal (ULN) are defined as clinically significant for this study. The central laboratory report will alert the Investigator if a subject meets this threshold. When a randomized subject who is receiving investigational product has an ALT or AST elevation beyond the clinical significant margin above, the Investigator should monitor the subject according to the instructions below and discontinue the subject from investigational product if a pre-specified criterion is met.

The Investigator should select the appropriate set of instructions (either A, B, or C below) for managing a subject with elevated liver enzymes based upon the following factors: (1) the magnitude of a subject's ALT or AST elevation, (2) the presence or absence of symptoms, (3) whether there is a corresponding increase in total bilirubin (TBL) \geq 2X ULN.

Investigator Instructions for Management of Subjects with ALT or AST \geq 3X ULN

A) Subject has:

- **ALT or AST ≥ 3 X ULN with TBL ≥ 2 X ULN and alkaline phosphatase (ALP) < 2 X ULN**

1. The subject should *interrupt* investigational product.
2. Refer to the “*Event of Clinical Interest (ECI) Guidance for Potential DILI (Drug-Induced Liver Injury) in Clinical Trials*” (located in the Investigator Trial File Binder or equivalent) and perform procedures accordingly.
3. If an etiology for the elevated ALT or AST and TBL levels is established and the abnormalities resolve, investigational product may be restarted with approval by the Sponsor. Otherwise, the subject should discontinue treatment with investigational product.

Note: Laboratory assessments prescribed in the *Event of Clinical Interest (ECI) Guidance for Potential DILI (Drug-Induced Liver Injury) in Clinical Trials* may be sent locally in emergent cases and to support subject compliance with the necessary evaluations. Subjects unwilling to undergo the prescribed testing should be discontinued from treatment with investigational product.

B) Subject has:

- **ALT or AST ≥ 8 X ULN *OR***
- **ALT or AST ≥ 3 X ULN and signs or symptoms of a drug reaction consistent with liver injury (eg, fever, eosinophilia, right upper quadrant pain, dark urine, fatigue, etc.)**

1. The subject should *interrupt* investigational product.
2. Perform repeat ALT and AST within 3 days of receipt of the laboratory report.
3. Initiate evaluation for potential causes. See Section II below.
4. Repeat ALT and AST tests at appropriate intervals, initially approximately 2-times per week, until resolution or return to baseline.
5. If an etiology for the elevated liver enzymes is established (eg, active hepatitis with specific etiology demonstrated, cholecystitis, biliary obstruction), investigational product may be restarted with approval by the Sponsor. Otherwise, the subject should discontinue treatment with investigational product.

Note: Local laboratory assessments can be used to support compliance with the repeat testing procedure described above if required. Subjects unwilling to undergo repeat ALT and AST testing at the frequency recommended above should be discontinued from treatment with investigational product.

C) Subject has:

- **ALT or AST $\geq 3X$ and $<8X$ ULN**

1. For subjects with:

ALT or AST $\geq 3X$ and $<5X$ ULN:

- Perform repeat ALT and AST within 3-5 days of receipt of the laboratory report.

OR

ALT or AST $\geq 5X$ ULN and $<8X$ ULN:

- Perform repeat ALT and AST within 3 days of receipt of the laboratory report. Subjects unable to undergo repeat measurements within 3 days must interrupt investigational product.

2. Initiate evaluation for potential causes. See Section II below.

3. Actions based upon *initial* repeat testing:

If **ALT or AST $\geq 3X$ ULN with TBL $\geq 2X$ ULN**, then interrupt investigational product and monitor as described in Section A Instructions above and also per "*Event of Clinical Interest (ECI) Guidance for Potential DILI (Drug-Induced Liver Injury) in Clinical Trials*" (located in the Investigator Trial File Binder or equivalent) and perform procedures accordingly.

If **ALT or AST $\geq 8X$ ULN or ALT or AST $\geq 3X$ ULN with symptoms** present (eg, fever, eosinophilia, right upper quadrant pain, dark urine, fatigue, etc.), then interrupt investigational product and monitor as described in Section B Instructions above.

If **ALT or AST $\geq 3X$ ULN and $<8X$ ULN** (without above criteria met), continue to measure ALT and AST 1- to 2-times per week (2-times per week if ALT or AST $\geq 5X$ ULN or if an increase $>20\%$ occurred since the first elevated value[s]).

If **ALT and AST $>$ ULN and $<3X$ ULN**, perform repeat determination in 5-7 days, and then at appropriate intervals (eg, every other week) until the subject's ALT and AST levels are within normal limits or are similar to baseline.

4. Actions based upon *follow-up* repeat testing:

If **ALT or AST $\geq 5X$ ULN** after 2 weeks, *discontinue investigational product*.

If **ALT or AST remain elevated** ($\geq 3X$ and $<5X$ ULN) but stable, the frequency of retesting can decrease (eg, every other week) with approval from the Sponsor.

If **ALT and AST $>$ ULN and $<3X$ ULN**, perform repeat determination in 5-7 days, and then at appropriate intervals (eg, every other week) until the subject's ALT and AST levels are within normal limits or are similar to baseline.

Note: Local laboratory assessments can be used to support compliance with the repeat testing procedures described above if required. Subjects unwilling to undergo repeat ALT and AST testing at the frequency defined above should be discontinued from treatment with investigational product.

In summary, subjects should be discontinued from investigational product for any of the following reasons:

- ALT or AST ≥ 3 X ULN with TBL ≥ 2 X ULN and ALP < 2 X ULN and without an established etiology.
- ALT or AST ≥ 8 X ULN or ≥ 3 X ULN with symptoms consistent with liver injury and without an established etiology.
- ALT or AST ≥ 5 X ULN for 2 weeks or longer.

Section II: Guidance for Assessment of Potential Etiology

Questions to Assess Etiology

Investigate potential causes for the subject's elevated liver enzymes using the questions below. Answers to the questions should be recorded in the subject's source documents and appropriate eCRFs.

1. Has the subject recently:
 - Had a change in his/her pattern of alcohol use? Investigate historic pattern of alcohol use as well.
 - Administered an illegal drug(s) (including intravenous drugs)?
 - Been exposed to a chemical agent or other environmental toxin?
 - Consumed any unusual foods (eg, mushrooms), seasonal foods, or initiated treatment with new herbal/nutritional supplements?
 - Initiated a new diet regimen, started a rigorous exercise program, or experienced any form of severe physical exertion?
 - Traveled to another country or region?
2. Does the subject have a relevant concomitant illness (eg, cholelithiasis, hepatitis, etc.) or has the subject had potential exposure to viral hepatitis (transfusion, tattoo, new sexual partner)?

3. Does the subject have a relevant medical history (eg, autoimmune disorder, cancer, Gilbert's syndrome, obesity, Wilson's disease, non-alcoholic steatohepatitis (NASH), alcoholic or infectious hepatitis, biliary tract disease, hypoxic/ischemic hepatopathy, etc.)?
4. Has the subject recently been treated with a concomitant medication(s) with demonstrated or suspected effects on the liver (eg, acetaminophen; amiodarone; aspirin; chlorpromazine; dantrolene; erythromycin; halothane; isoniazid; methyldopa; nitrofurantoin; oxyphenisatin; perhexiline maleate; phenytoin; propylthiouracil; rifampin; sulfonamides; tetracyclines) or initiated treatment with another new medication(s)?

Additional Laboratory/Imaging Evaluations

In subjects for whom an etiology for the abnormal liver enzymes is unknown or whose elevated liver enzymes persist for more than 1-week:

1. Consider performing serologic tests including: (a) Hepatitis A (IgM); (b) Hepatitis B (surface antigen and core IgM); (c) Hepatitis C (antibody); (d) Hepatitis E (IgG and IgM). Obtain consent prior to testing, if required locally. Additional evaluations may be performed at the discretion of the Investigator.
2. Consider an ultrasound of the subject's right upper quadrant and additional scans (endoscopic retrograde cholangiopancreatography [ERCP] or magnetic resonance cholangiopancreatography [MRCP]) if needed.

Note: Subjects may also be referred to a gastroenterologist or hepatologist for an additional work-up if considered necessary by the Investigator.

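### Section 8.7, instruction C: the repeat liver test orders only ALT and AST, but the interruption rule applied to that repeat also needs total bilirubin

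*Combined protocol and SAP*

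**What the plan says.** Section 8.7 sends a subject with ALT or AST at or above 3 times ULN to instruction A, B or C, according to the size of the elevation, symptoms, and whether total bilirubin (TBL) has reached 2 times ULN. Instruction A also requires alkaline phosphatase (ALP) below 2 times ULN.

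Instruction C covers ALT or AST from 3 to below 8 times ULN:

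- **Step 1, 3 to below 5 times ULN:** "Perform repeat ALT and AST within 3-5 days of receipt of the laboratory report".
- **Step 1, 5 to below 8 times ULN:** "Perform repeat ALT and AST within 3 days of receipt of the laboratory report", with the added rule "Subjects unable to undergo repeat measurements within 3 days must interrupt investigational product".
- **Step 3, acting on the initial repeat:** if ALT or AST is at least 3 times ULN with TBL at least 2 times ULN, "then interrupt investigational product and monitor as described in Section A Instructions above". If neither the bilirubin branch nor the high-enzyme or symptom branch is met and the enzymes are still 3 to below 8 times ULN, "continue to measure ALT and AST 1- to 2-times per week".
- **Step 4:** discontinue if ALT or AST is still at least 5 times ULN after 2 weeks. For stable values of 3 to below 5 times ULN, "the frequency of retesting can decrease (eg, every other week) with approval from the Sponsor".
- **Closing note:** "Local laboratory assessments can be used to support compliance with the repeat testing procedures described above if required".

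The summary list in 8.7 makes ALT or AST at least 3 times ULN, TBL at least 2 times ULN and ALP below 2 times ULN, with no cause established, a reason to discontinue. The second event of clinical interest in 8.6 uses the same three laboratory thresholds and counts unscheduled tests.

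**The concern.** A rule that interrupts study drug for subject safety should be decidable from the tests ordered to feed it. Here the first step 3 branch turns on bilirubin, and so does the continue-testing branch, because it applies only when the earlier branches are not met. Bilirubin is not in the order, and the text gives no default for when it is unknown.

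A subject whose enzymes stay at a moderate level while bilirubin rises could therefore remain on drug with the rise unseen. The 8.6 event, reportable within 24 hours, could not be recognised from an ALT and AST repeat either.

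**Working it through.** The protocol states no figure to reproduce. The check compares the tests ordered with the tests each rule needs, then uses the visit schedule for the time to the next ordered bilirubin.

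**1. Tests ordered against tests needed**

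| Rule | Laboratory inputs needed | Ordered at the C repeat | Missing |
|---|---|---|---|
| 8.7 C step 3, first branch (interrupt) | ALT/AST, TBL | ALT, AST | TBL |
| 8.7 C step 3, continue testing | ALT/AST, TBL (to exclude the first branch) | ALT, AST | TBL |
| 8.7 summary list, first discontinuation reason | ALT/AST, TBL, ALP | ALT, AST | TBL, ALP |
| 8.6 event of clinical interest, item 2 | ALT/AST, TBL, ALP | ALT, AST | TBL, ALP |

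**2. Whether other text supplies the missing test**

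- Follow-up testing in steps 3 and 4 and the closing note name only ALT and AST.
- The cause evaluation (8.7 Section II) lists serology and imaging to consider and does not name bilirubin. Beyond that, "Additional evaluations may be performed at the discretion of the Investigator".
- Within instruction C, the separate drug-induced liver injury guidance is invoked only once the bilirubin criterion is met, so that reference cannot prompt the measurement.
- TBL and ALP are in the Table 5 chemistry panel, so they are known for a first sample drawn at a scheduled chemistry visit. A subject with TBL at least 2 times ULN and ALP below 2 times ULN in that sample already falls under instruction A. The step 3 branch therefore serves mainly to catch a later rise.

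**3. Example (hypothetical values)**

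First sample: ALT 4 times ULN, TBL 1.8 times ULN, no symptoms, so instruction C applies. At the repeat, ALT is still 4 times ULN and TBL is 2.2 times ULN. Step 3 calls for interruption. With only ALT and AST in hand, the site sees a case for continued testing.

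**4. Time to the next ordered bilirubin**

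The Schedule of Activities places chemistry at Day 1 and Weeks 6, 12, 18 and 26, and at rescue or early termination visits.

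- Elevation found on Day 1, Week 6 or Week 12: 6 − 0 = 12 − 6 = 18 − 12 = 6 weeks.
- Elevation found at Week 18: 26 − 18 = 8 weeks.
- With ±7 days at both post-randomization visits: 42 ± 14 = 28 to 56 days (4 to 8 weeks), and 56 ± 14 = 42 to 70 days (6 to 10 weeks). Section 6 calls the windows recommended rather than required, so these are not firm limits.

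The plan intends this decision at a repeat due within 3 to 5 days of the laboratory report. A rescue or early termination visit would shorten the gap. For a subject who stays at 5 times ULN or above, the 2-week discontinuation rule limits it to about 2 weeks.

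**The case against.** The strongest reply is that this is a slip of wording with little practical effect. Step 3 tells the Investigator to act on TBL at the initial repeat, and 8.7 uses TBL to choose between instructions, so a physician following the text would see that it is needed. Section 7 makes the central laboratory the default, local testing is allowed only if required, and all four analytes sit in one Table 5 panel. The liver injury guidance and laboratory manual are not among the documents and may specify bilirubin. All of this stands, and it limits how often the gap would matter. It does not put the test into the order, and an evident intention to use TBL argues for writing it in.

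Four stronger readings are tempting, and the documents do not support them.

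- **The rule can never be applied, or bilirubin would never be measured.** The text only fails to order it. A subject with TBL at least 2 times ULN and ALP also at least 2 times ULN in the first sample does not meet instruction A and can enter C with a high TBL already known.
- **Bilirubin is the only thing that stops drug at 3 to below 5 times ULN.** Eosinophilia is a listed trigger, grouped with symptoms, and section 6.6.1 item 8 lets the Investigator stop product for any condition that puts the subject at risk. TBL is the main laboratory criterion for a symptom-free subject in this band.
- **No bilirubin criterion applies after the initial repeat.** Step 4 has none, but the instruction selection and the summary list in 8.7 are not confined to the initial repeat.
- **Only instruction C is affected.** Instruction B's repeats also name only ALT and AST. Less depends on it there, because B has already interrupted product.

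**Conclusion.** The mismatch is on the face of the text: instruction C orders two tests, and the interruption rule for the same repeat needs a third. The summary discontinuation reason and the 8.6 event need a fourth, ALP.

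If a site runs only what is ordered, a bilirubin rise after the first sample may go unseen for nominally 6 to 8 weeks in a symptom-free subject who stays at 3 to below 5 times ULN. That figure assumes an elevation found at a scheduled chemistry visit, no rescue or early termination visit in between, and no bilirubin added by the laboratory or by unseen guidance. If repeats are run as a full chemistry panel, the gap is nil.

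The case should be rare. Exclusion criterion 22 removes subjects with AST or ALT above 2 times ULN at screening, or total bilirubin above 1.5 times ULN unless they have Gilbert's. The documents give no expected frequency, so none is offered here. No efficacy analysis is affected. This is an inexpensive improvement to a subject-safety instruction, and nothing here shows that subjects would be harmed.

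**What to change.** In section 8.7 instruction C, order ALT, AST, total bilirubin and ALP at the step 1 repeat and at each follow-up test in steps 3 and 4, and state that this holds when a local laboratory is used. Make the same change to the instruction B repeats for consistency. Add one sentence telling sites to check the existing bilirubin criteria in 8.6 and 8.7 at every repeat. The thresholds need no change: the step 3 trigger can stay without an ALP condition, and the summary discontinuation list can stay as written.

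The cost is a wording change, a site clarification, and two added analytes per repeat sample. Both analytes are already in the Table 5 chemistry panel, and no extra visit or blood draw is needed.
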